5.2.3. IND Sponsor Reporting to the FDA

It is the responsibility of the IND Sponsor to make the determination of which SAEs are “serious and unexpected suspected adverse reactions” (SUSARs) as defined in 21 CFR 312.32.

- *Suspected adverse reaction* means any AE for which there is a reasonable possibility that the drug caused the AE.
- *Unexpected Adverse Event* means an AE that is not listed in the Investigator’s Brochure or is not listed at the specificity or severity that has been observed.

All SUSARs, as determined by the IND Sponsor, will be reported to FDA as IND Safety Reports; IND Safety Reports will be provided to all participating Investigators by the IND Sponsor or delegated CRO.

The IND Sponsor will also submit an IND Annual Report of the progress of the investigation to the FDA as defined in 21 CFR 312.33.

5.3. Reporting to Site IRBs and Relevant Regulatory Agencies

Each site IoR is responsible for reporting AEs, unanticipated problems, protocol deviations and non-compliance to the site IRB and other relevant country regulatory authorities in accordance with their institutional and country requirements for reporting.

Site-specific data reports will be made available through the data management contractor to facilitate expedited and continuing review reporting requirements.

Only the IND Sponsor will submit reports to the U.S. FDA. If the IND Sponsor submits an IND Safety Report to the U.S. FDA, these will be provided to all sites with instruction as to whether or not any actions need to be taken, such as amendment of consent. Investigators must maintain documentation of compliance with actions required for IND safety reports.

5.3.1. Regulations Applicable to the French Study Sites Only

This section applies only to sites in Martinique and Guadeloupe who follow regulatory oversight by the French ANSM.

The sponsor will be responsible for reporting all Serious Adverse Reactions (SARs) to the ANSM and the Ethics Committee (CPP SOOM 4) in accordance with the local laws and regulations requirement (L. 1123-10, R. 1123-38 and following of the Public Health Code). In addition, SUSARs that are reported to the FDA as IND Safety Reports will be reported to the ANSM and the Ethics Committee (CPP SOOM 4) with 7 days or 15 days depending on the severity (according to Article R. 1123-47 of the Public Health Code). The legal representative of the sponsor in the EU will inform the ANSM of VRC 704 study pauses and the decision to resume or close the study following a study pause.

5.4. Data and Safety Monitoring Board

The PSRT (see [Section 8.8](#)), will have the primary responsibility for the real-time oversight of safety data and SAE reviews. The NIAID Intramural Data and Safety Monitoring Board

(DSMB) will review cumulative study data twice per year to evaluate safety, study conduct, and scientific validity and integrity of the trial and will be consulted if there is a study pause as required by Section 4.6 of the protocol.

The DSMB members will assess the timeliness, completeness, and accuracy of the data submitted to them for review and whether the data are sufficient for evaluation of the safety and welfare of study participants. The DSMB Executive Secretary will be provided with a sealed copy of the randomization codes needed for the DSMB review of the safety data. The DSMB will also assess the performance of overall study operations and any other relevant issues, as necessary. Following each review, the DSMB will provide its recommendations to the study sponsor, including whether the study should continue without change, be modified, or be terminated.

6. STATISTICAL CONSIDERATIONS AND SAMPLE ANALYSIS

6.1. Overview

This study is a multi-center trial to assess the safety and immunogenicity of a 2-injection schedule of VRC-CHKVLP059-00-VP or PBS placebo injections at Days 0 and 28. The primary objective relates to safety and tolerability; the secondary and exploratory objectives concern immunogenicity and incidence of Chikungunya infection.

6.2. Endpoints

6.2.1. Safety

Assessment of product safety will include clinical observation and monitoring of hematological and chemical parameters. Reactogenicity will be closely monitored for 7 days after injection and safety evaluated by clinical visits through the study duration of 72 weeks.

The following parameters will be assessed:

- Local reactogenicity signs and symptoms for 7 days after each injection
- Systemic reactogenicity signs and symptoms for 7 days after each injection
- Laboratory measures of safety through 4 weeks after last injection
- Adverse events through 4 weeks after last injection
- Serious adverse events and new chronic medical conditions throughout the study
- CHIKV infection events throughout the study

6.2.2. Immunogenicity

The principle immunogenicity endpoints are measured at Week 0 and 8 by neutralization assay. Exploratory immunogenicity endpoints are measured at Week 4, 16, 24, 48, and 72 by neutralization assay, ELISA, and other exploratory research tests.

6.3. Sample Size and Accrual

The study design is to enroll 400 healthy adult participants ages 18 to 60 that reside in CHIKV endemic areas. Randomization will equally allocate subjects to vaccine or placebo schedules with stratification by ages 18-40 and 41-60 years. The enrollment plan does not include provision for replacing subjects with incomplete injections or visit schedules.

Enrollments may occur rapidly at more than one site. The data management CRO will carefully monitor study enrollment and notify all sites and the VRC Protocol Chair when the completion of enrollment is near.

The sample size for this study was not selected to test a formal null hypothesis. It reflects the number of vaccine doses that are available for the study and the desire to gain maximal information for the conduct of possible Phase 3 follow on trials. This latter consideration is particularly important as reliable estimates of CHIKV incidence in the target population, vaccine effects and logistical considerations in implementing future trials must be understood prior to a Phase III trial. Nevertheless, power computations are provided below as an indication of the probability of observing results of interest.

There are not good data to estimate the loss to follow-up rate for this study. The power calculations assume a 10% loss in both groups for the primary and secondary endpoints. Loss to follow-up for the exploratory outcomes are likely to be larger but are not included as power calculations are not included for these outcomes.

6.3.1. Power Calculations for Evaluation of Safety

The goal of the safety evaluation for this study is to identify safety concerns associated with injections of the investigational vaccine. Two sample size calculations for safety are expressed in terms of two approaches, within group and comparing two groups.

1. The ability to detect safety or reactogenicity events within each injection group:

The ability of the study to identify safety events may be expressed in terms of the probability of observing one or more event of interest (e.g., AEs) assuming a range of “true” but unknown event rates. The power to observe one or more event in a single group of 180 subjects is 83.62% when the true rate is 1.0% and 97.37% when the true rate is 2.0% (Table 3).

Table 3: Probability of Observing One or More Safety Events within a Group (n=180)

True Event Rate	Pr (1 or more events)
0.01%	1.78%
0.10%	16.48%
0.33%	45.17%
0.50%	59.43%
1.00%	83.62%
2.00%	97.37%

1. The minimum detectable difference in safety event (e.g., AEs) rates for comparing two injection groups using Fisher’s exact test:

Safety event rates may vary considerably with the type of event considered therefore a wide range of possible rates is considered for comparison by vaccine group (Table 4).

Table 4: Minimum Detectable Differences in Event Rates for Power = 80% or 90% Assuming Type I Two-Tail Error Rate of 5% (n=180 per Group)

Power	Assumed Event Rate in Group 1 (n=180)	Minimum Detectable Event Rate Group 2 (n=180)	Difference in Rates
80%	0.1%	5.5%	5.4%
	1.0%	7.5%	6.5%
	5.0%	14.2%	9.2%
	25%	39.3%	14.3%
90%	0.1%	6.9%	6.8%
	1.0%	8.9%	7.9%
	5.0%	16.0%	11.0%
	25%	41.6%	16.6%

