5 SAMPLE SIZE CONSIDERATIONS

The study design is to enroll 400 healthy adult participants ages 18 to 60 that reside in CHIKV endemic areas. Randomization will equally allocate subjects to vaccine or placebo schedules with electronic stratification by ages 18-40 and 41-60 years. The enrollment plan does not include provision for replacing subjects with incomplete injections or visit schedules.

Enrollments may occur rapidly at more than one site. The sample size for this study was not selected to test a formal null hypothesis, rather it reflects the number of vaccine doses that are available for the study and the desire to gain maximal information for the possible conduct of Phase 3 follow on trials. There are not good data to estimate the loss to follow-up rate for this study. The power calculations assume a 10% loss in both groups for the primary and secondary endpoints.

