5.1 Power Calculations for Evaluation of Safety

The goal of the safety evaluation for this study is to identify safety concerns associated with injections of the investigational vaccine. Two sample size calculations for safety are expressed in terms of two approaches, within group and comparing two groups.

1. The ability to detect safety or reactogenicity events within each injection group:

The ability of the study to identify safety events may be expressed in terms of the probability of observing one or more event of interest (e.g., AEs) assuming a range of “true” but unknown event rates. The power to observe one or more event in a single group of 180 subjects is 83.62% when the true rate is 1.0% and 97.37% when the true rate is 2.0% (Table).

Table 2: Probability of Observing One or More Safety Events within a Group (n=180)

True Event Rate	Pr (1 or more events)
0.01%	1.78%
0.10%	16.48%
0.33%	45.17%
0.50%	59.43%
1.00%	83.62%
2.00%	97.37%

2. The minimum detectable difference in safety event (e.g., AEs) rates for comparing two injection groups using Fisher’s exact test:

Safety event rates may vary considerably with the type of event considered therefore a wide range of possible rates is considered for comparison by vaccine group (Table).

Table 3: Minimum Detectable Differences in Event Rates for Power = 80% or 90% Assuming Type I Two-Tail Error Rate of 5% (n=180 per Group)

Power	Assumed Event Rate in Group 1 (n=180)	Minimum Detectable Event Rate Group 2 (n=180)	Difference in Rates
80%	0.1%	5.5%	5.4%
	1.0%	7.5%	6.5%
	5.0%	14.2%	9.2%
	25%	39.3%	14.3%
90%	0.1%	6.9%	6.8%
	1.0%	8.9%	7.9%
	5.0%	16.0%	11.0%
	25%	41.6%	16.6%

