6.8 Multiple Comparisons/Multiplicity

This study is not designed to test a specific hypothesis. Rather it is intended to obtain sufficient data to design and implement future efficacy trials. Absent the testing of a formal primary hypothesis there is no requirement for multiple comparison adjustments.

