8.3.2 Unsolicited Adverse Events

All unsolicited AEs will be recorded in the study database from receipt of first study injection through 4 weeks after the last study injection administered. At subsequent follow-up visits, only SAEs and new chronic medical conditions will be recorded through the last study visit.

The proportion of subjects reporting at least one unsolicited AE will be summarized by MedDRA system organ class and preferred term for each injection, age stratum, and treatment group and over all injections. Denominators for percentages are the number of subjects who received the injection being summarized. A 95% CI will be presented along with a Fisher's exact test comparing the treatment groups and testing the difference in the proportion of subjects reporting an unsolicited AE for each MedDRA system organ class and preferred term (**Table 14.3.1.6, Appendix I**).

Unsolicited AEs by subject will be presented in **Listing 16.2.7.2, Appendix III**.

The following summaries for unsolicited AEs will be presented by MedDRA system organ class (SOC), preferred term, dose, age stratum, treatment group, and site:

- *Subject level summary of severity and relationship to study product (**Tables 14.3.1.7.1-14.3.1.7.2, Appendix I**);*
- *Subject incidence of AEs over time (Days 1-7, Days > 7) (**Tables 14.3.1.8.1-14.3.1.8.2, Appendix I**);*
- *Total frequency of AEs over time (Days 1-7, Days > 7) (**Table 14.3.1.9, Appendix I**);*
- *Subject listing of non-serious AEs of moderate or greater severity (**Table 14.3.2.2, Appendix I**);*
- *Bar chart of non-serious AEs by severity and MedDRA SOC (**Figure 14.3.1.2, Appendix II**);*
- *Bar chart of non-serious AEs by severity (**Figure 14.3.1.3, Appendix II**);*
- *Bar chart of non-serious AEs by relationship to study product and MedDRA SOC (**Figure 14.3.1.4, Appendix II**);*

- *Bar chart of non-serious AEs by relationship to study product (Figure 14.3.1.5, Appendix II).*

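### Protocol Table 4 (SAP Table 3) is labelled as Fisher's exact test but holds an undisclosed continuity-corrected normal approximation, which understates power for rare events by 4.2 to 10.5 points (conservative, minor)

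*Combined protocol and SAP*

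**What the plan says.** Protocol section 6.3.1 gives two views of the power of the safety evaluation. The second, Table 4, is introduced as "The minimum detectable difference in safety event (e.g., AEs) rates for comparing two injection groups using Fisher’s exact test". The table title sets a two-tailed 5% error rate, 80% or 90% power and 180 subjects per group. For Group 1 event rates of 0.1, 1, 5 and 25%, the printed Group 2 rates are 5.5, 7.5, 14.2 and 39.3% (80% power) and 6.9, 8.9, 16.0 and 41.6% (90% power). SAP section 5.1 reprints the same eight rates as Table 3, again described as "rates for comparing two injection groups using Fisher’s exact test". Neither place mentions an approximation or a continuity correction.

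Fisher's test is also the planned analysis. SAP section 8.3.2 specifies a Fisher's "exact test comparing the treatment groups and testing the difference in the proportion of subjects reporting an unsolicited AE" by system organ class and preferred term.

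Protocol section 6.3 explains the 180: "The power calculations assume a 10% loss in both groups for the primary and secondary endpoints". It also says what the figures are for: "power computations are provided below as an indication of the probability of observing results of interest".

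**The concern.** A reader who takes the label at its word and computes the power of Fisher's exact test cannot reproduce most of the table. For rare events the gap is plain. Table 4 is the only between-arm power statement for the primary (safety) objective, and uncommon adverse events are where someone planning a later trial would look. If the method behind the numbers differs from the test named, the table misdescribes the trial's sensitivity, and the size and direction of the gap need to be known.

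**Working it through.** **Inputs.** From protocol section 6.3.1 and SAP section 5.1: n = 180 per group, two-sided α = 0.05, power 80% and 90%, Group 1 rate p1 = 0.1, 1, 5, 25%, and the eight printed Group 2 rates p2.

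**Step 1: reproduce the printed rates.** Solve for p2 in the continuity-corrected, pooled-variance normal formula:

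power = Φ{ [ (p2 − p1) − 1/n − 1.96·√(2p̄(1 − p̄)/n) ] / √[ (p1(1 − p1) + p2(1 − p2))/n ] }, with p̄ = (p1 + p2)/2.

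Example, p1 = 0.1%, 80% power. At p2 = 5.513%, p̄ = 2.807% and p2 − p1 = 0.05413. The numerator is 0.05413 − 0.00556 − 1.96 × 0.01741 = 0.01445 and the denominator is 0.01717. The ratio is 0.842, the normal quantile for 80%.

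All eight solutions:

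| Power | p1 | Formula p2 | Printed p2 |
|---|---|---|---|
| 80% | 0.1% | 5.51% | 5.5% |
| 80% | 1% | 7.48% | 7.5% |
| 80% | 5% | 14.23% | 14.2% |
| 80% | 25% | 39.30% | 39.3% |
| 90% | 0.1% | 6.89% | 6.9% |
| 90% | 1% | 8.93% | 8.9% |
| 90% | 5% | 15.95% | 16.0% |
| 90% | 25% | 41.56% | 41.6% |

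Every cell matches after rounding. The uncorrected, unpooled and arcsine forms match none, and a continuity-corrected arcsine form also fails (4.59% against 5.5% in the first cell).

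**Step 2: power of the named test at the printed rates.** List all 181 × 181 outcomes, mark those with two-sided Fisher p ≤ 0.05, and sum their binomial probabilities.

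The first cell can nearly be done by hand. With 0 events in Group 1, Fisher rejects from 6 events in Group 2 (p = 0.030; with 5, p = 0.061). With 1 event it rejects from 8 (p = 0.037; with 7, p = 0.067). With 2 events it rejects from 10 (p = 0.035; with 9, p = 0.061). At 0.1% against 5.5%:

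0.8352 × 0.9344 + 0.1505 × 0.7782 + 0.0135 × 0.5327 = 0.7804 + 0.1171 + 0.0072 = 0.905.

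**Step 3: smallest p2 at which Fisher reaches the stated power.** Find the root, then round up to 0.1 point so that the printed rate attains the power.

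| Power | p1 | Printed p2 | Fisher power at printed p2 | Exact minimum | Rounded up | Printed too high by |
|---|---|---|---|---|---|---|
| 80% | 0.1% | 5.5% | 90.5% | 4.64% | 4.7% | 0.8 |
| 80% | 1% | 7.5% | 85.4% | 6.96% | 7.0% | 0.5 |
| 80% | 5% | 14.2% | 81.4% | 14.02% | 14.1% | 0.1 |
| 80% | 25% | 39.3% | 80.2% | 39.27% | 39.3% | 0 |
| 90% | 0.1% | 6.9% | 97.6% | 5.44% | 5.5% | 1.4 |
| 90% | 1% | 8.9% | 94.2% | 8.10% | 8.2% | 0.7 |
| 90% | 5% | 16.0% | 91.6% | 15.64% | 15.7% | 0.3 |
| 90% | 25% | 41.6% | 90.3% | 41.51% | 41.6% | 0 |

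In the 0.1% row, the 5.5% printed for 80% power is the smallest 0.1-point rate that reaches 90%. Defining the two-sided p-value by summing the less probable tables or by doubling one tail gives the same power in all eight cells.

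**Step 4: check the replacements.** Power at the rounded-up rates is 81.0, 80.5, 80.6, 80.2% and 90.5, 90.6, 90.3, 90.3%. At 0.1 point lower it is 79.4, 79.4, 79.8, 79.6% and 89.6, 89.99, 89.8, 89.96%. Each replacement is therefore the minimum at printed precision.

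**Step 5: the gap in terms of sample size.** At the printed rates, Fisher's test reaches and keeps the stated power from about 150 per group (0.1 against 5.5%), 162 (1 against 7.5%), 140 (0.1 against 6.9%) and 158 (1 against 8.9%), not 180.

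**The case against.** The continuity-corrected formula is a customary approximation to Fisher power, so the label can be read as naming the test and not the computing method. On that reading the table contains no slip; it lacks a footnote. It is true that no arithmetic slip was made. But a reader told only the name of the test cannot tell that the low-rate cells are loose, so the lack of disclosure matters there.

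Nothing in the trial depends on the table. SAP section 5 states "The sample size for this study was not selected to test a formal null hypothesis, rather it reflects the number of vaccine doses", and SAP section 6.8 states "This study is not designed to test a specific hypothesis". The pause rules in protocol section 4.6 rest on related serious and Grade 4 events. The approximation also errs on the safe side. All of this stands and keeps the point minor.

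The 180 is itself a loose assumption. Unsolicited-event denominators are subjects who received the injection, so first-injection comparisons would use about 200 per group. There the exact minimums, to the nearest 0.1 point, are about 4.2, 6.5, 13.4 and 38.5% (80%) and 4.9, 7.5, 14.9 and 40.6% (90%). In the 5% and 25% rows that shift (0.6 to 0.9 points) exceeds the whole correction (0 to 0.3). This is a fair argument for settling for a footnote. It does not make the table right at the n it states, and the 10% loss is a declared assumption that is not criticised here.

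Finally, the shell for comparing solicited events (SAP Table 14.3.1.5) uses differences with confidence intervals and no Fisher p-value. The table therefore bears mainly on unsolicited events.

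**Conclusion.** The point holds and is minor. Table 4 and its SAP copy name Fisher's exact test, but all eight rates come from a continuity-corrected normal approximation that neither document discloses. At Group 1 rates of 0.1% and 1% the approximation understates the power of the named test by 10.5 and 5.4 points (80% entries) and by 7.6 and 4.2 points (90% entries). The corresponding detectable rates are overstated by 0.5 to 1.4 percentage points. The 5% and 25% rows are within 2 points of the stated power and are not in dispute. Since the trial can detect somewhat smaller differences than printed, no reader is promised sensitivity it lacks. The result rests on n = 180 per group, equal allocation, a two-sided 5% level and independent binomial counts, all as the table assumes.

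**What to change.** Make one of these changes in both Protocol Table 4 and SAP Table 3.

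- **Exact values.** For 80% power print 4.7, 7.0, 14.1 and 39.3% (differences 4.6, 6.0, 9.1 and 14.3 points). For 90% print 5.5, 8.2, 15.7 and 41.6% (differences 5.4, 7.2, 10.7 and 16.6 points). Add a footnote: *Smallest Group 2 rate, to 0.1 percentage point, at which the two-sided Fisher's exact test reaches the stated power, by exact enumeration.* Six rates change; both 25% entries stay. Replacing only the four cells in the 0.1% and 1% rows (4.7, 7.0; 5.5, 8.2%) would cover the cells that matter.
- **Footnote only.** Keep the numbers and add: *Continuity-corrected normal approximation; at Group 1 rates of 1% or less it understates the power of Fisher's exact test by about 4 to 11 points.*

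The footnote is the smallest sufficient change. Either option edits one table that appears in two documents and leaves the design, sample size and analysis as they are.

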6.3.2. Power Calculations for Evaluation of Immune Responses

A secondary objective is to evaluate the humoral immunogenicity of VRC-CHKVLP059-00-VP by neutralization assay at 4 weeks after the final 20 mcg dose (Week 8). Vaccine specific neutralization antibodies are not anticipated in the non-vaccinated group. Therefore, direct comparison between the active and placebo group is of minimal value in assessing sample size. Preliminary Phase 1 neutralization data suggest that neutralization results at the visit with peak response are log-normally distributed with a mean and standard deviation on the log-scale of 7.41 and 0.67 respectively. This standard deviation is rounded up to 0.70 and two more conservative options of 1.0 and 1.5 result in 95% confidence intervals (CI) for GMT (Table 5).

Table 5: 95% Confidence Interval for GMT Neutralization among Vaccinees at Time of Peak Response (n=180 per Group)

Assume Standard Deviation on Log Scale	95% CI for GMT Neutralization Among Vaccinees (n=180) at Time of Peak Response
0.70	(1490.7, 1831.7)
1.0	(1426.6, 1914.1)
1.5	(1324.8, 2061.1)

The study is not designed to compare two groups defined by baseline covariates such as gender or age strata. However, the following table is included to provide a sense of the power available for such comparisons. The simple case of two groups (e.g., male and female), assuming equal participation (i.e., 90 subjects for each gender-vaccine group), is given in Table 6 for comparing response rates.

Table 6: Detectable Geometric Mean Ratio between Two Groups for Power = 80% or 90% Assuming Type I Two-Tail Error Rate of 5% (n=90 per Group)

Power	Standard Deviation	Detectable
-------	--------------------	------------

	on Log Scale	Geometric Mean Ratio (n=90 per group)
80%	0.7	1.34
	1.0	1.52
	1.5	1.88
90%	0.7	1.40
	1.0	1.63
	1.5	2.08

6.4. Statistical Analysis

Study enrollment is defined in this protocol as being randomized and receiving the first study injection. All enrolled subjects will receive at least one injection and therefore will provide some safety data. The safety population will include all enrolled subjects, summarized according to the actual vaccination received.

The Intent-to-treat (ITT) population will include all enrolled subjects, analyzed according to the randomized vaccine. The Per Protocol (PP) analyses will include all subjects receiving two vaccinations within window as assigned by the randomization schedule, and not experiencing any other major protocol deviations prior to their Week 8 visit. The PP analyses will also include subjects determined to be CHIKV infected prior to the receipt of their scheduled second vaccination and not experiencing any other major protocol deviations prior to their date of infection. Subjects will be censored from the immunogenicity analysis following CHIKV infection. The Modified intent-to-treat (mITT) analyses will include all enrolled subjects with evaluable immunogenicity data at their week 8 visit, without exclusions for protocol deviations or censoring for CHIKV infection. Additional cohorts may be defined in the Statistical Analysis Plan (SAP).

No formal multiple comparison adjustments will be employed. Imputation of missing values is not planned. They may be implemented for secondary or tertiary outcomes if supported by the data and if sufficient consequence to justify their inclusion. Analysis variables include baseline, safety, reactogenicity, and immunogenicity variables for primary and secondary objective analyses, respectively. Exploratory analyses will estimate CHIKV infection rates, and evaluate additional immunogenicity assays.

In general, descriptive statistics by vaccine group will be tabulated for all variables of interest, stratified by age as is appropriate. This will include point estimates (mean, geometric mean, median or proportions) and their respective 95% CI or percentile spread. Formal comparisons will use standard methods, contingency tables for categorical variables, t-tests or non-parametric analogs for comparing means or geometric means, logistic regression and analysis of covariance for model discrete and continuous variables respectively.

